3.2 Power for primary endpoint

The sample size justification considers the probability of success of the study based on the success criterion for the planned sample size. The success criterion for one CFZ533 treatment arm (see Section 2.4.2) is reached if

$$P(\theta_{\rm CFZ533} - \theta_{\rm control} < 0.15 | data) > 0.8,$$

[figure not shown]
where θ is the composite efficacy failure rates, and the prior is Beta(1/3, 1/3).

Table 3-2 and Figure 3-2 show the probability of success of the study for a sample size of 48 participants in the CFZ533 arm and 32 participants in the control arm for a range of underlying event rates for composite efficacy failure and serious infections in the CFZ533 treatment arm and in the control arm. A control rate of 10% at Month 12 is expected based on (Levitsky et al 2017), which examined a large registry of deceased donor liver transplant participants from Scientific Registry of Transplant Recipients (SRTR) and internal Novartis studies (RAD001 Study H2304 and AEB071 Study B2203).

of CFZ533 arm and 32 participants of control arm			
$\theta_{ m CFZ533}$	$ heta_{ ext{control}}$	Probability of success	
0.07	0.070	0.971	
0.07	0.103	0.986	
0.07	0.135	0.993	
0.07	0.168	0.997	
0.07	0.200	0.999	
0.11	0.070	0.833	
0.11	0.103	0.904	
0.11	0.135	0.947	
0.11	0.168	0.973	
0.11	0.200	0.987	
0.15	0.070	0.594	
0.15	0.103	0.729	
0.15	0.135	0.830	
0.15	0.168	0.900	
0.15	0.200	0.944	

Table 3-2Probability of success under different event rates for 48 participants
of CFZ533 arm and 32 participants of control arm

3.3 Power for key secondary variable

The primary analysis of renal function is based on the FAS. Participants continue to be followed after study drug discontinuation and participants with graft loss or death will have their Month 12 values imputed as described in Section 2.5.3. For treatment comparisons, there will be a

Novartis	For business use only	Page 35
SAP		CCFZ533A2202

randomized sample of 48 and 32 participants in the CFZ533 and control arms respectively after 12 months. Assuming a common standard deviation of 16 mL/min and one-sided $\alpha = 0.10$, there is 63, 73, or 81% power to detect a difference of 6, 7, or 8 mL/min/1.73m² respectively. If the standard deviation is 20, there is 51, 59, or 67% power respectively. The power calcuation is completed by nQuery 8.4 based on two-sample *t*-test with equal variance.

4 Change to protocol specified analyses

Not applicable.

5 Appendix

5.1 Analysis visit windows

Analysis visit windows will be used to summarize the data by visit and are defined in terms of weeks. These will be based on the study schedule of evaluation and comprised a set of days "around" the nominal visits. Analysis visit windows are non-overlapping. All together they cover the entire study period. They are aligned to the dosing regimen, which is every 2 weeks, meaning a month is targeted to cover 4 weeks or 28 days.

As participants do not necessarily have their examinations at the exact scheduled time, it might be misleading if all data with the same nominal visit number are lumped together for a by-visit analysis. Thus, all data (including reported unscheduled assessments) are "re-aligned" according to the window schema given below. Note that the visit windows defined in the protocol are used to guide investigators whereas the 're-aligned' analysis visit windows (simply called visit windows in the following) will be used for the analyses.

Re-aligned visit	Visit window	Relative to first treatment date			
	(relative to date of Tx)	Start day of Visit window	Midpoint	End day of visit window	
1	Screening	Day of informed consent		Day of transplant 1	
2	Baseline	Day of Tx		Day of Tx	
3	Randomization	Day of Tx +1		Start of study drug [#] = Day 1	
4	Day 15	2	8	11	
5	Day 22	12	15	18	
6	Day 29	19	22	29	
7	Month 1.5	30	36	43	
8	Month 2	44	50	57	
9	Month 2.5	58	64	71	
10	Month 3	72	78	85	
11	Month 3.5	86	92	99	
12	Month 4	100	106	113	

Table 5-1	Analysis	visit	windows

For business use only

Novartis SAP

Re-aligned visit	Visit window	Relativ	e to first treatme	ent date
	(relative to date of Tx)	Start day of Visit window	Midpoint	End day of visi window
13	Month 4.5	114	120	127
14	Month 5	128	134	141
15	Month 5.5	142	148	155
16	Month 6	156	162	190
17	Month 8	191	218	246
18	Month 10	247	274	302
19	Month 12	303	330	372 (358*)
20	Month 15	373	414	456
21	Month 18	457	498	540
22	Month 21	541	582	624
23	Month 24	625	666	708
24	Month 27	709	750	792
25	Month 30	793	834	876
26	Month 33	877	918	960
27	Month 36	961	1002	1044
28	Month 39	1045	1086	1128
29	Month 42	1129	1170	1212
30	Month 45	1213	1254	1296
31	Month 48	1297	1338	1380
32	Month 51	1381	1422	1464
33	Month 54	1465	1506	1548
34	Month 57	1549	1590	1632
35	Month 60	1633	1674	1716
36	Month 63	1717	1758	1800
37	Month 66	1801	1842	1884
38	Month 69	1885	1926	1968
39	Month 72	1969	2010	End of study

Day 1 = randomization day if a participant was randomized but did not receive study drug.

* For all Month 12 analyses, the end of visit window of Month 12 visit is Day 358, instead of Day 372.

Under this window schema, multiple records of a participant are re-aligned into the same visit as follows:

- For post-randomization continuous values (except for CFZ533, TAC, and MMF trough level measurements and liver tests), for a given participant, if multiple numeric measurements for a given variable are reported in the same visit window (e.g., Month 6), then the measurement closest to the target visit day will be taken; if tie, take the earlier measurement. For screening visit, the target day is day of transplant – 1; for baseline, day of transplant; for randomization, start of study drug (Day 1); for other visits, the midpoint of the visit window.
- For trough levels, the last value observed within a visit window is taken.

- For liver tests (bilirubin, SGOT, SGPT, GGT, and alkaline phosphatase), the following algorithm is applied:
 - a. If an acute rejection occurs within a visit window with multiple liver tests reported, the time of the event is the date rejection first suspected, and the liver test to be summarized are the closest to that event (if tie, take the earlier one)
 - b. If no rejection occurs, the assessment closest to the target day is taken.
- For categorical values, the worst value of all records observed in the visit window is used.

For parameters which are not collected at every scheduled visit

, visit windows defined in Table 5-1 will be combined using the following rules for an applicable visit post randomization: "lower limit" of the combined window= "upper limit of prior applicable visit" + 1, "upper limit" of the combined window = "target day of current visit" + integer part of [("target day of next applicable visit" – "target day of current visit")/2]. For example, if a parameter is measured only at Randomization, Day 29 (Month 1), Month 3, Month 6, and Month 12, the combined Day 29 (Month 1) visit window will be from Day 2 to Day 50 (= Day 22 + interger part of [(78 - 22)/2]), Month 3 will extend from Day 51 to Day 120 (= Day 78 + interger part of [(162 - 78)/2]), etc.. If more than one assessment falls into the combined window, the rules defined above handling multiple records are applied.

5.2 Imputation rules

Although not the rule, partially or completely missing dates occur. Known dates with this issue are the start date on the Medical History eCRF page, start and end dates on the Concomitant Medications eCRF page, or Surgical and Medical Procedures page eCRF page, and occasionally the start and end dates on the Adverse Events eCRF.

Any date incompletely reported is split into its day, month, and year components. In SAS, a numerical date value can only be defined if all these date components are known; incomplete dates are to be handled as text strings (character-type variables); as such, they could not be easily processed. An imputation rule for incomplete dates will be performed.

5.2.1 Study drug

Not applicable.

5.2.2 AE date imputation

This algorithm is expressed in the Variable Source Derivation column as **#IMPUTAEV**(*event*) where *event* is the partial start date of the adverse event.

Table 5-2 explains the notation used in the logic matrix. Please note that **missing start dates** will not be imputed.

Note, if the imputed AE (or CM) start is after AE (or CM) end date, then set AE (or CM) start equal to AE (or CM) end date. Missing AE end dates will not be imputed.

Table 5-2 Imputation logic for partial AE dates

	Day	Month	Year
Partial Adverse Event (or Concomitant Medication) Start Date	Not used	MON	YYYY
Treatment Start Date (TRTSDT)	Not used	TRTM	TRTY

The following matrix explains the logic behind the imputation.

	MON MISSING	MON < TRTM	MON = TRTM	MON > TRTM
YYYY MISSING	NC	NC	NC	NC
YYYY < TRTY	(D)	(C)	(C)	(C)
YYYY = TRTY	(B)	(C)	(A)	(A)
YYYY> TRTY	(E)	(A)	(A)	(A)

The following table is the legend to the logic matrix.

Relationship	
Before Treatment Start	Partial date indicates AE (or CM) start date prior to Treatment Start Date
After Treatment Start	Partial date indicates AE (or CM) start date after Treatment Start Date
Uncertain	Partial date insufficient to determine relationship of AE (or CM) start date to Treatment Start Date
Imputation Calculation	n
NC / Blank Uncertain	No convention
(A) After Treatment Start or Uncertain	MAX(01MONYYYY, TRTSDT+1)
(B) Uncertain	TRTSDT+1
(C) Before Treatment Start	15MONYYYY
(D) Before Treatment Start	01JULYYYY

(E) After Treatment01JANYYYYStart01JANYYYY

5.2.3 Concomitant medication date imputation

Table 5-3 explains the notation used in the logic matrix. Missing end dates will not be imputed.

Table 5-3 Imputation logic for partial concomitant medication dates

	Day	Month	Year
Partial Conmed. end Date	Not used	MON	YYYY
Last Contact Date (LASTDT)	Not used	LSTM	LSTY

	MON MISSING	MON < LSTM	MON = LSTM	MON > LSTM
YYYY MISSING	NC	NC	NC	NC
YYYY < LSTY	(C)	(A)	(A)	(A)
YYYY = LSTY	(B)	(A)	(B)	(A)
YYYY > LSTY	(C)	(A)	(A)	(A)

Relationship	
Before Last contact date	Partial date indicates CM end date prior to Last Contact Date
After Last contact date	Partial date indicates CM end date after Last Contact Date
Uncertain	Partial date insufficient to determine relationship of CM end date to Last Contact Date
Imputation Calculatio	n
NC / Blank Uncertain	No convention
(A) Before/After Last contact date	Last day MONYYYY
(B) Uncertain	LASTDT

(C) Before/After	31DECYYYY
Last contact date	

At the interim analysis, if the above logic is applied and the imputed end date is after the cut-off date, then the imputed end date will be replaced with the cut-off date.

5.3 Laboratory parameters derivations

Table 5-4 presents criteria to define expanded limits and notable abnormalities of key laboratory tests.

Laboratory variable	Standard units	SI units		
Liver function and related variables				
AST (SGOT)	≥3 × ULN	≥3 × ULN		
ALT (SGPT)	≥3 × ULN	≥3 × ULN		
Bilirubin	>2 × ULN	>2 × ULN		
Alkaline Phosphatase	≥5 × ULN	≥5 × ULN		
GGT	≥5 × ULN	≥5 × ULN		
Renal function, metabolic and electrolyte variables				
Urea	≥5 × ULN	≥5 × ULN		
Creatinine	After Day 8±2: ≥3 mg/dL OR	After Day 8±2: ≥265 µmol/L OR		
	>30% above value	>30% above value		
	from preceding visit	from preceding visit		
Uric acid	M ≥12 mg/dL	M ≥714 µmol/L		
	F ≥9 mg/dL	F ≥535 µmol/L		
Glucose	<45 mg/dL	<2.5 mmol/L		
	>250 mg/dL	>13.9 mmol/L		
Cholesterol	≥350 mg/dL	≥9.1 mmol/L		
Triglycerides	≥750 mg/dL	≥8.5 mmol/L		
CK (MB)	None	None		
Potassium	≤3.0 mEq/L	≤3 mmol/L		
	≥ 6.0 mEq/L	≥ 6 mmol/L		
Calcium	≤ 6 mg/dL	≤ 1.5 mmol/L		
	≥ 13 mg/dL	≥ 3.2 mmol/L		
Magnesium	< 1.0 mg/dL	< 0.4 mmol/L		
	> 3.6 mg/dL	> 1.5 mmol/L		
Amylase	≥ 2 × ULN	≥ 2 × ULN		
Lipase	≥ 2 × ULN	≥ 2 × ULN		
Hematology variables				
Hemoglobin	<7 g/dL	<4.39 mmol/L		
Platelets (thrombocytes)	<50 k/mm ³	<50 × 10 ⁹ /L		
	≥700 k/mm³	≥700 × 10 ⁹ /L		
Leukocytes (WBCs)	≤2.0 k/mm³	≤ 2.0 × 10 ⁹ /L		
· · ·	≥16 k/mm³	≥16 × 10 ⁹ /L		
Hematology variables: differential				

 Table 5-4
 Clinically notable lab abnormalities

Novartis	For business use only	Page 41
SAP		CCFZ533A2202
Granulocytes (poly, neutrophils)	≤1,000/mm³	≤1 x 10 ⁹ /L
Eosinophils	≥12%	≥12%

≤1,000/mm³

≤1× 10⁹/L

Conversion factors from standard (US) units into SI units are given in Table 5-5.

Laboratory Variable	Standard Unit	Conversion Factor*	SI Unit
Platelets	%	1	%
Hematocrit	%	1	%
Hemoglobin	g/dL	0.6206	mmol/L
RBC	10 ⁶ /mm ³	1	10 ¹² /L
WBC	10 ³ /mm ³	1	10 ⁹ /L
Sodium	mEq/L	1	mmol/L
Potassium	mEq/L	1	mmol/L
Chloride	mEq/L	1	mmol/L
Calcium	mg/dL	0.2495	mmol/L
Magnesium	mg/dL	0.4114	mmol/L
	mEq/L	0.5	mmol/L
norganic phosphate	mg/dL	0.3229	mmol/L
Urea**	Urea[mg/dL]	0.1665	mmol/L
Creatinine	mg/dL	88.4	µmol/L
Glucose	mg/dL	0.05551	mmol/L
HbA1c	%	1	%
Uric acid	mg/dL	0.05948	mmol/L
AST (SGOT)	U/L	1	U/L
ALT(SGPT)	U/L	1	U/L
Alkaline phosphatase	U/L	1	U/L
GGT	U/L	1	U/L
Total bilirubin	mg/dL	17.1	umol/L
Fotal cholesterol	mg/dL	0.02586	mmol/L
High Density Lipoprotein(HDL)	mg/dL	0.02586	mmol/L
∟ow Density ∟ipoprotein(LDL)	mg/dL	0.02586	mmol/L
Triglycerides	mg/dL	0.01129	mmol/L
Creatinine phosphokinase CK)	U/L	1	U/L
_ipase	U/L	1	U/L
Amylase	U/L	1	U/L
Albumin	g/dL	10	g/L
Protein	g/dL	10	g/L
Urinary protein:creatinine	mg/g	0.113	mg/mmol

Table 5-5 Conversion Factors from Standard (US) into SI units

Lymphocytes

Table 5-6 displays the liver events to be displayed. Refer to the internal Novartis "Analysis plan for liver safety data" for more information.

Table 5-6 Newly occurring liver enzyme abnormalities

Safety set

Timepoint: Week xx/Endpoint/Any time post-baseline

	Active dose A N=xxx n/m (%)		Active dose B N=xxx n/m (%)		Placebo N=xxx n/m (%)	
LT > 3x ULN	 xx/xxx	(xx.x)	 	(xx.x)	 xx/xxx	(xx.x)
LT > 5x ULN	xx/xxx	(xx.x)	xx/xxx	(xx.x)	xx/xxx	(xx.x)
LT > 8x ULN	xx/xxx	(xx.x)	xx/xxx	(xx.x)	xx/xxx	(xx.x)
LT > 10x ULN	xx/xxx	(xx.x)	xx/xxx	(xx.x)	xx/xxx	(xx.x)
LT > 20x ULN	xx/xxx	(xx.x)	xx/xxx	(xx.x)	xx/xxx	(xx.x)
JT or AST > 3x ULN	xx/xxx	(xx.x)	xx/xxx	(xx.x)	xx/xxx	(xx.x)
LT or AST > 5x ULN	xx/xxx	(xx.x)	xx/xxx	(xx.x)	xx/xxx	(xx.x)
LT or AST > 8x ULN	xx/xxx	(xx.x)	xx/xxx	(xx.x)	xx/xxx	(xx.x)
LT or AST > 10x ULN	xx/xxx	(xx.x)	xx/xxx	(xx.x)	xx/xxx	(xx.x)
ST or AST > 20x ULN	xx/xxx	(xx.x)	xx/xxx	(xx.x)	xx/xxx	(xx.x)
LT or AST > 3x ULN & TBL > 1.5x ULN	xx/xxx	(xx.x)	xx/xxx	(xx.x)	xx/xxx	(xx.x)
LT or AST > 3x ULN & TBL > 2x ULN	xx/xxx	(xx.x)	xx/xxx	(xx.x)	xx/xxx	(xx.x)
T or AST > 5x ULN & TBL > 2x ULN	xx/xxx	(xx.x)	xx/xxx	(xx.x)	xx/xxx	(xx.x)
T or AST > 8x ULN & TBL > 2x ULN	xx/xxx	(xx.x)	xx/xxx	(xx.x)	xx/xxx	(xx.x)
T or AST > 10x ULN & TBL > 2x ULN	xx/xxx	(xx.x)	xx/xxx	(xx.x)	xx/xxx	(xx.x)
T or AST > 20x ULN & TBL > 2x ULN	xx/xxx	(xx.x)	xx/xxx	(xx.x)	xx/xxx	(xx.x)
T or AST > 3x ULN & INR > 1.5x ULN	xx/xxx	(xx.x)	xx/xxx	(xx.x)	xx/xxx	(xx.x)
P > 1.5x ULN	xx/xxx	(xx.x)	xx/xxx	(xx.x)	xx/xxx	(xx.x)
LP > 2x ULN	xx/xxx	(xx.x)	xx/xxx	(xx.x)	xx/xxx	(xx.x)
JP > 3x ULN	xx/xxx	(xx.x)	xx/xxx	(xx.x)	xx/xxx	(xx.x)
P > 5x ULN	xx/xxx	(xx.x)	xx/xxx	(xx.x)	xx/xxx	(xx.x)
BL > 1x ULN	xx/xxx	(xx.x)	xx/xxx	(xx.x)	xx/xxx	(xx.x)
BL > 1.5x ULN	xx/xxx	(xx.x)	xx/xxx	(xx.x)	xx/xxx	(xx.x)
BL > 2x ULN	xx/xxx	(xx.x)	xx/xxx	(xx.x)	xx/xxx	(xx.x)
BL > 3x ULN	xx/xxx	(xx.x)	xx/xxx	(xx.x)	xx/xxx	(xx.x)
LP > 3x ULN & TBL > 2x ULN	xx/xxx	(xx.x)	xx/xxx	(xx.x)	xx/xxx	(xx.x)
LP > 5x ULN & TBL > 2x ULN	xx/xxx	(xx.x)	xx/xxx	(xx.x)	xx/xxx	(xx.x)
LT or AST > 3x ULN & TBL > 2x ULN						
& ALP < 2x ULN	xx/xxx	(xx.x)	xx/xxx	(xx.x)	xx/xxx	(xx.x)
ALT or AST > 3x ULN & TBL > 2x ULN						
& ALP < 2x ULN) or reported Hy's Law case	xx/xxx	(xx.x)	xx/xxx	(xx.x)	xx/xxx	(xx.x)
LT or AST > 3x ULN & (nausea or						
vomiting or fatique or general malaise or						
abdominal pain or (rash and eosinophilia))	xx/xxx	(xx.x)	xx/xxx	(xx.x)	xx/xxx	(xx.x)

Newly occurring: Subjects not meeting criterion at baseline and meeting criterion post-baseline m = Number of subjects at risk (subjects having a baseline measurement not meeting the criterion or missing but at least one post-baseline measurement for the laboratory test(s) <and timeframe> under consideration)

n = Number of subjects at risk who satisfy the criterion <at post-baseline visit, endpoint, or any time> post-baseline

Notes:

"Hy's law case" is a lower level term in MedDRA (10070546) and may be reported as AE. Only new onsets will be considered.
 The event which combines lab information and signs/symptoms information is derived using LB and the liver events eCRF, but is not using the AE dataset. Even if in the FDA 2009, they added as a PT anorexia, the choice was to kept it out from our definition as too unspecific.

3. Black (mandatory): Those mentioned in the FDA guidance (section 2). The last one is mandatory if liver eCRFs are used. 4. Black (mandatory) and italic: Additional criteria mentioned in the Novartis Hepatotox guideline (section 5.1).

Page 43

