5.1 Inclusion criteria

Participants eligible for inclusion in this study must meet **all** of the following criteria:

Screening period up to liver transplantation

- 1. Written informed consent must be obtained before any assessment is performed.
- 2. Male or female subject between 18-70 years of age.
- 3. Recipient of a primary liver transplant from a deceased donor.
- 4. Up to date vaccination as per local immunization schedules.
- 5. Recipient tested negative for Human Immunodeficiency Virus (HIV).
- Model for End stage Liver Disease (MELD) score ≤ 30 (based on laboratory values, using the United Network for Organ Sharing (UNOS) MELD calculator: https://unos.org/resources/allocation-calculators/).
- 11. Transplantation to occur within defined screening period following informed consent signature.

At Randomization (Day 8±2)

- Recipients with no active Hepatitis C Virus (HCV) and Hepatitis B (HBV) replication. Recipients with HCV antibody positive should have no detectable HCV-RNA. Recipients with Hepatitis B infection should have no detectable HBV DNA. Cases of spontaneous HCV clearance should be discussed with sponsor.
- Allograft is functioning at an acceptable level by the time of randomization as defined by AST, ALT, Alkaline Phosphatase levels ≤ 5 times ULN and Total Bilirubin ≤ 2 times ULN.
- 9. Renal function (eGFR, MDRD-4 formula) \geq 30 mL/min/1.73m² based on most recent post-transplant value prior to randomization.
- 10. Recipients who have been initiated on an immunosuppressive regimen that contains TAC, MMF and corticosteroids as per protocol.

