Infections													A	As req	uired												
Hepatocellular carcinoma													A	As req	uired												
Malignancies													A	As req	uired												
Withdrawal of Informed Consent													A	∖s req	uired												
M12 Period completion ⁹													As re	equire	d												х

Page 77 of 136 Protocol No. CCFZ533A2202

Period														Treatr	nent							
Visit Name																						
Month		1 1.5 2 2.5 3 3.5 4 4.5 5 5.5 6 or FU 6.5 7 7.5 8 or FU 8.5 9 9 10 or FU 10.5 11 11.5 12 or FU																				
Day		1 1.5 2 2.5 3 3.5 4 4.5 5 5.5 FU 5.5 / 7.5 FU 5.5 9.5 OF 10.5 11 11.5 FU FU FU F															337					
Hour (h)	Pre	0	EOI +1h																			
Study completion ⁹													A	As req	uired							

@ = all assessment must be completed prior to the liver transplantation procedure.

S = Assessment to be recorded in source documentation, not in CRF.

X = Assessment to be performed/evaluated and recorded in CRF if applicable.

= to be performed once in a 48-hour period if Screening and Transplantation (Day 1) occur in close proximity.

EOI = End of infusion IV (administration), EOS = End of Study, EOT = End of Treatment

0 = Assessment can be done at home for Arm 1 participants and for Arm 2 and 3 participants receiving CFZ533 at home via a health care provider.

1. Graft vascular patency must be confirmed using appropriate imaging technology (e.g. Doppler ultrasound, angiography, angio MRI). Participants with any thrombosis or occlusion of hepatic artery, veins, portal vein or inferior vena cava or participants with no confirmatory imaging study cannot be randomized.

2. Assessment and specification refers to the physical examination. See Table 8-4 for detailed list of expected physical examinations.

3. Site must perform, at minimum, all assessments needed to evaluate participant's eligibility at screening and randomization.

4. Safety laboratory tests (central) from Baseline, Day 8±2 (Randomization), and at all visits indicated will include hematology, chemistry, coagulation and urinalysis as specified in Table 8-5. A-fetoprotein will be evaluated at Baseline, Day 8±2/Randomization (for HCC subjects, only) and as needed thereafter for recurrent and *de novo* cases. MMF trough levels will be collected at all visits indicated or unscheduled visit (dose change). At the time of biopsies, a chemistry central laboratory test should be performed and thereafter until the final outcome.

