2.1.1 General definitions

For the purposes of statistical analysis, "study treatments" are and will be displayed in the outputs as CFZ533 300mg + MMF, CFZ533 600mg + MMF, and TAC + MMF. "Baseline" is defined as the last assessment, including unscheduled assessments, performed prior to liver Tx. All assessments obtained after liver Tx are considered as post-baseline unless otherwise specified. Only centrally adjudicated data will be used for efficacy analyses and laboratory (including vital signs).

In the event that a participant only takes one of the three treatments, the following definitions apply:

- Start of study treatment:
 - a. CFZ533 arms: day of the first loading dose of CFZ533 on Day 8±2 post-LTx.
 - b. Control arm: Day 8 post LTx.
- End of study treatment:
 - a. CFZ533 arms: day of the last dose of CFZ533 +14 days. If a participant in CFZ533 arms discontinues treatment before Day 8±2 (first dose of CFZ533), the rules of control arm apply.
 - b. Control arm: day of the last dose of TAC.

In calculating the duration of treatment, days of permitted interruption of study medication (CFZ, TAC, and MMF) for any reason will be included (see Section 6.5 in the Protocol for details on permitted dose interruption). The entire treatment period is divided into three parts: Treatment Period 1, 2, and 3 (see Section 1.1).

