2.7.3 Laboratory data

Analyses of laboratory data include data since baseline (liver Tx) but changes are calucated based on the day of randomization. Summary statistics (mean, standard deviation, minimum, median, maximum, and 25% and 75% percentiles) of quantitative lab variables, including change from randomization, will be provided by parameter, treatment, and visit. Similarly, proportion of notable abnormalities of key laboratory tests (Table 5-4) by parameter, treatment, and visit and its listing will be provided. Shift tables using the normal/abnormal classification will be used to compare randomization to the worst on-treatment value.

The following lab parameters will be presented: liver function (AST, ALT, GGT, ALP, and total bilirubin), renal function (eGFR, creatinine, and urine protein/creatinine ratio), lipids, and hematology (WBC, neutrophils, and lymphocytes). eGFR will also be summarized by CKG stages (< 15, [15, 30), [30, 45), [45, 60), [60, 90), and \geq 90) by treatment arm and by visit.

Liver events will be presented as defined in Table 5-6.

Average duration of infection-free period will be presented by treatment. The frequency of following categories will also be summarized by treatment:

- EBV: > 2000 copies/mL;
- CMV: ≤ 5000, (5000, 1000], and > 10000 copies/mL;

For CFZ533 participants, the counts will be provided separately for participants who remain on CFZ533 vs. those who switch from CFZ533 to discontinuation or to SOC. In participants who switch from CFZ533, summary statistics of the mean time from the end of switch to viral load elevation (EBV > 2000 copies/mL, CMV > 10000 copies/mL) will be provided. A listing of participants above the thresholds will be provided by treatment and visit. The day of end of switch is the same as the day of discontinuation of CFZ533 (defined in Section 2.1.1).

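### SAP Table 5-6 counts newly occurring liver abnormalities against the pre-transplant native liver instead of the graft as it stood at randomization

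*SAP*

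**What the plan says.** SAP 2.7.3 hands the liver output to one table: "Liver events will be presented as defined in Table 5-6". The notes under that table (SAP 5.3) define the event as "Newly occurring: Subjects not meeting criterion at baseline and meeting criterion post-baseline". They define the denominator m as participants whose baseline value did not meet the criterion, or was missing, and who have a later measurement.

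The table does not say what baseline means. SAP 2.1.1 does: baseline "is defined as the last assessment, including unscheduled assessments, performed prior to liver Tx", and "All assessments obtained after liver Tx are considered as post-baseline unless otherwise specified". The protocol schedule agrees. A footnote to Table 8-1 says of the baseline visit that "all assessment must be completed prior to the liver transplantation procedure".

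The graft is assessed later. Criterion 8 in Protocol 5.1 applies at randomization (Day 8±2). It holds AST and ALT to the same limit as alkaline phosphatase: "Alkaline Phosphatase levels ≤ 5 times ULN and Total Bilirubin ≤ 2 times ULN".

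Elsewhere the SAP uses randomization as its laboratory reference. Sections 2.1 and 2.7.3 calculate changes from the day of randomization, and the shift tables in 2.7.3 compare randomization with the worst on-treatment value.

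**The concern.** The table should show whether a graft that was acceptable at randomization deteriorated on study treatment. With the native liver as reference, it shows whether the graft later crosses a threshold that the explanted organ had not crossed. The mismatch works in two ways.

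- **Lost from the at-risk set.** A recipient with bilirubin above 2×ULN before surgery drops out of m for that row and can never be a new event, although criterion 8 required bilirubin at or below 2×ULN in the graft. The same happens in a combined row if the combination was met before surgery.
- **Counted as new when it is not.** Criterion 8 allows ALT up to 5×ULN. A graft at 4×ULN before the first dose that stays there on treatment is a newly occurring value above 3×ULN whenever the pre-transplant value was at or below 3×ULN, or missing.

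This is the first study of CFZ533 in liver recipients (Protocol 1.1). Table 5-6 is the only display in the SAP that identifies new onset at multiples of ULN, and the only one that combines ALT/AST with bilirubin.

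**Working it through.** Table 5-6 is an empty shell, so the plan has no figure to reproduce. The check classifies its rows and then illustrates the two faults under stated assumptions.

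**Step 1. Which rows does criterion 8 rule out at randomization?** A row is ruled out if it needs ALT or AST above 5×ULN or more, ALP above 5×ULN, or bilirubin above 2×ULN or more.

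| Rows | Total | Ruled out | Still possible |
|---|---|---|---|
| ALT alone (>3, 5, 8, 10, 20×) | 5 | 4 | 1 |
| ALT or AST (same thresholds) | 5 | 4 | 1 |
| ALT/AST >3× with TBL >1.5× | 1 | 0 | 1 |
| ALT/AST (five thresholds) with TBL >2× | 5 | 5 | 0 |
| ALT/AST >3× with INR | 1 | 0 | 1 |
| ALP (>1.5, 2, 3, 5×) | 4 | 1 | 3 |
| TBL (>1, 1.5, 2, 3×) | 4 | 2 | 2 |
| ALP with TBL >2× | 2 | 2 | 0 |
| ALT/AST >3×, TBL >2×, ALP <2× (two versions) | 2 | 2 | 0 |
| ALT/AST >3× with symptoms | 1 | 0 | 1 |
| **All** | **30** | **20** | **10** |

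The classification is approximate. Eligibility uses local values up to 3 days old (Protocol 8.4.1), while SAP summaries use central values. One version of the ALT/AST, TBL and ALP row also admits a case reported as an adverse event.

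**Step 2. Inputs for the illustrations.** Planned N is 48 per CFZ533 arm and 32 in control (Protocol 6.1.3). The following are assumptions:
- p: share meeting the criterion before transplant
- r: share meeting it at randomization
- s: share of those who still meet it afterwards
- q: true new-onset rate, set at 10%

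With independence, the SAP rule gives m = N(1−p) and n = m[rs + (1−r)q]. The randomization rule gives m = N(1−r) and n = mq.

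**Step 3. First fault, TBL >2× row (r about 0).**

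| p | SAP m (N=48) | SAP n | SAP m (N=32) | SAP n |
|---|---|---|---|---|
| 10% | 43.2 | 4.32 | 28.8 | 2.88 |
| 30% | 33.6 | 3.36 | 22.4 | 2.24 |
| 50% | 24.0 | 2.40 | 16.0 | 1.60 |
| 70% | 14.4 | 1.44 | 9.6 | 0.96 |

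With the randomization reference the results are 4.80/48 and 3.20/32. Under independence n and m fall together and the percentage stays at 10%, so the loss is of participants and precision. If later event rates differ, say q1 in those who met the criterion before transplant and q0 in the rest, the SAP shows q0 and the whole arm has p·q1 + (1−p)·q0. The percentage is then off by p(q1−q0), which is zero only when q1 = q0.

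**Step 4. Second fault, ALT >3× row (N=48, p=0).**

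| r | SAP, s=0.5 | SAP, s=1 | Randomization reference |
|---|---|---|---|
| 10% | 48(0.05+0.09) = 6.7 (14%) | 48(0.10+0.09) = 9.1 (19%) | 4.3/43.2 (10%) |
| 30% | 48(0.15+0.07) = 10.6 (22%) | 48(0.30+0.07) = 17.8 (37%) | 3.4/33.6 (10%) |
| 50% | 48(0.25+0.05) = 14.4 (30%) | 48(0.50+0.05) = 26.4 (55%) | 2.4/24.0 (10%) |

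Here the percentage itself is inflated. The percentages are the same for N=32.

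**Step 5. Data window.** SAP 2.1 says laboratory tables include data since transplantation. SAP 2.1.2 and 2.7 limit safety analyses to on-treatment data unless otherwise specified, and 2.7 excepts baseline data. Under the wider window the Day 8 pre-dose value is itself post-baseline and counts without persisting, which corresponds to the s=1 column. Under the on-treatment window only a persisting elevation counts. The first fault is present under either.

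**The case against.** Four arguments can be made for the plan.

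1. **Other outputs cover much of the ground.** SAP 2.7.3 reports notable abnormalities by parameter, treatment and visit, with a listing. The Table 5-4 thresholds (AST/ALT at or above 3×ULN, bilirubin above 2×ULN, ALP and GGT at or above 5×ULN) carry no pre-transplant exclusion. This stands. A reader might infer that bilirubin events in the sickest recipients disappear from the report; they do not. Table 5-4 does not, however, show new onset or combined patterns, and the shift tables use only a normal/abnormal split.

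2. **Table 5-6 is a generic shell.** It has placebo columns in a trial without placebo, and SAP 5.3 refers to an internal liver-safety plan that is not among these documents. A programmer might carry over the randomization convention for changes. That is possible, but an at-risk rule is not a change score, and nothing in the table departs from the definition in 2.1.1. As written, the pre-transplant value governs.

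3. **The on-treatment restriction removes run-in values.** If it governs, it does. It leaves persisting elevations and the lost denominators untouched.

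4. **The reference precedes randomization and one rule applies to all arms.** This stands. A reader might infer that the comparison between arms is biased, or that every count is wrong. The documents show neither: no direction follows from the rule, and rows such as ALT above 20×ULN may barely move.

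**Conclusion.** The concern holds as a defect in a descriptive safety table, of moderate severity. The stated rule takes the explanted liver as reference, contrary to the SAP's own laboratory convention. It removes at-risk participants in rows that criterion 8 rules out at randomization, and it can count pre-existing graft elevations as new in the other 10. The effect falls mainly on the combined ALT/AST plus bilirubin rows and on new-onset counts.

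The size is unknown. The documents give no pre-transplant or Day 8 laboratory distributions; p, r, s and q are assumptions, and 48/48/32 are planned numbers in a trial that SAP Section 1 says was terminated early. A reader might infer that the fault must be cured before the trial can be interpreted. The documents do not support that: the primary endpoint, the eGFR endpoint and the stopping rules (BPAR with RAI ≥6, and serious infections) do not use this table.

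**What to change.** Add a note to Table 5-6 that:
- sets the reference as the last central value at or before the first study dose (randomization day in control);
- defines m as participants not meeting the row's criterion at that point who have at least one later value;
- counts n only from later on-treatment samples, and so settles SAP 2.1 against 2.1.2 and 2.7 for this table;
- states how a missing reference value is handled, since the present rule puts such participants at risk;
- applies the same reference to the combined rows.

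The cost is a short SAP note and a changed reference flag in programming. Central chemistry is already scheduled at Day 8±2 (Protocol Table 8-1), and SAP Table 5-1 already has a randomization window ending at the start of study drug. No further data are needed.
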